### **Viral serology**

All patients will be tested for Hepatitis B (HBsAg), HCV, CMV at Screening, earlier tests  $\leq$  6 months are acceptable. Any HIV positive patients will be excluded. If results are not available at Baseline, the patient may be included. However, an assessment has to be performed immediately. If results of a newly initiated assessment will be positive, the patient will subsequently be dropped from the study and administered the standard care provided by the center.

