### **Exclusion Criteria**

1. HIV positive patients.
2. Patients who are recipients of multiple solid organ or islet cell tissue transplants, or have previously received an organ or tissue transplant.
3. Patients with renal failure or CKD/ESRD who require renal replacement therapy for more than 2 weeks prior to transplantation.
4. History of malignancy of any organ system within the past 5 years whether or not there is evidence of local recurrence or metastases, other than non-metastatic basal or squamous cell carcinoma of the skin or HCC (see next criteria).
5. HCC that does not fulfill Milan criteria (1 nodule  $\leq$  5 cm, 2-3 nodules all  $\leq$  3 cm) at the time of transplantation.
6. Patients with a known hypersensitivity to the drugs used on study or their class, or to any of the excipients.
7. Patients receiving drugs known to significantly interact with any immunosuppressant used in the trial.
8. Patients who are recipients of AB0 incompatible transplant grafts.
9. Patients with a current systemic infection or sepsis requiring active use of IV antibiotics.
10. Patients with symptoms of significant mental illness and with inability to cooperate or communicate with the investigator. Patients who are unlikely to comply with the study requirements, or who are unable to give informed consent.
11. Women
  - o who are pregnant or breast feeding (pregnancy defined as the state of a female after conception and until the termination of gestation, confirmed by a positive hCG laboratory test ( $> 5$  mIU/ml)).

- who are menstruating and capable of becoming pregnant\* and not practicing a medically approved method of contraception (Pearl Index <1\*\*) during and up to at least 4-8 weeks after the end of treatment. A negative pregnancy test (serum) for all women entering menarche is required with sufficient lead time before inclusion.  
\*definition of post-menopausal: 12 months of natural (spontaneous) amenorrhea or 6 months of spontaneous amenorrhea with serum FSH levels >40 mIU/m or 6 weeks post surgical bilateral oophorectomy with or without hysterectomy  
\*\*examples of particularly reliable methods with Pearl Index (PI) <1, according to guidelines of Deutsche Gesellschaft für Gynäkologie und Geburtshilfe:
  - Combination pill with estrogen and gestagen (no mini-pill, PI=0.1-0.9)
  - Vaginal ring (NuvaRing®, PI=0.65 uncorr.; 0.4 corr.)
  - Contraceptive patch (EVRA®, PI= 0.72 uncorr.; 0.9 corr.)

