## 6.4 Treatment assignment

At Baseline (Visit 2), which has to take place prior to randomization, all patients who meet the inclusion and do not fulfill any of the exclusion criteria will be given the lowest available number on the randomization list of the respective stratum. This number assigns them to one of the treatment arms. The investigator will enter the randomization number on the CRF.

The randomization numbers will be generated using the following procedure to insure that treatment assignment is unbiased and concealed from patients and investigator staff. A

randomization list will be produced under the responsibility of the Novartis Nürnberg GCP Officer using a validated system that automates the random assignment of treatment arms to randomization numbers in the specified ratio. Randomization will be stratified by HCV status (positive/negative) and lab MELD (Model of End Stage Liver Disease) score below/equal or above 30 at transplantation.

Randomization of individual patients will be performed centrally by a CRO. Allocation of a patient to one of the two treatment groups will be performed in the following steps.

1. Information about patient enrolment (Screening Visit):

Study sites will inform the CRO about each patient inclusion via fax

2. Randomization (Baseline Visit):

At day of randomization, the site will provide the information of eligible patient to the CRO by fax.

The CRO will allocate the patient the next free consecutive randomization number allocated to the site. Randomization number and allocated treatment (according to the randomization list) will be provided to the site by fax.

The randomization number will be entered on the CRF of an individual patient.

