#### **6.6.8 Study completion and post-study treatment**

For all patients who were included into this study (i.e., who signed informed consent and are randomized), whether discontinued the study treatment prematurely or completed the study, the final examination 12 months after randomization (Visit 9) will be performed.

The investigator also must provide follow-up medical care for all patients who are prematurely withdrawn from the study, or must refer them for appropriate routine care according to center practice.

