### **Screening Visit - Visit 1 (day -21 to Tx)**

1. Patient signs informed consent.
2. Patient's eligibility for the study according to in- and exclusion criteria will be checked.
3. Demographic data will be recorded (sex, age, ethnic origin).
4. Relevant medical history will be obtained and recorded until time point of randomization.
5. Transplantation information will be recorded (donor and recipient information).
6. A complete physical examination will be performed.
7. Vital signs will be measured.
8. Venous blood will be drawn for measurement of viral serology (HBsAg, HCV).
9. Venous blood will be drawn for CMV monitoring (including pp65 Ag).
10. Venous blood will be drawn for HCV monitoring: Viral load (RNA level), HCV genotype (only at screening)
11. Menopausal status will be recorded and in all women of childbearing potential a pregnancy test will be performed ( $\beta$ -HCG) (see also section 7.3).
12. An intraoperative biopsy (preferably after reperfusion) will be performed for analysis of allograft fibrosis (only HCV positive patients).

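### The Viral serology paragraph (Protocol 7.6.4) lets patients be randomized with an unnamed result outstanding and removes them from the study if it is positive, contradicting Month 12 follow-up of all randomized patients

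*Protocol*

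**What the plan says.** The Viral serology paragraph of Protocol 7.6.4 opens by requiring HBsAg, HCV and CMV tests at Screening and accepts tests up to 6 months old. It continues: "Any HIV positive patients will be excluded". Next comes: "If results are not available at Baseline, the patient may be included". A test must then be done at once, and: "If results of a newly initiated assessment will be positive, the patient will subsequently be dropped from the study".

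Other sections bear on this rule:

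- **Eligibility.** Exclusion criterion 1 in Protocol 5.1 reads "HIV positive patients". Protocol 6.4 gives a randomization number only to patients who fulfil no exclusion criterion.
- **Stratification.** Protocol 6.4: "Randomization will be stratified by HCV status (positive/negative"), together with the lab MELD score.
- **Scheduled serology.** At Visit 1: "Venous blood will be drawn for measurement of viral serology (HBsAg, HCV"), with CMV monitoring as a separate item.
- **Follow-up.** Protocol 6.6.8 covers everyone who consented and was randomized, whether or not treatment stopped early: "the final examination 12 months after randomization (Visit 9) will be performed". The Everolimus part of 6.6.3 says the same of all randomized patients.
- **Stopping drug.** Protocol 5.2 says that stopping study drug is not study withdrawal. Positive serology is not among its mandatory reasons for stopping.

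**The concern.** Eligibility should be settled before allocation, and a randomized patient should then be followed whatever is learned later. This paragraph reverses that order. It permits entry with a result outstanding and ends participation on a result obtained after allocation, in an open-label trial.

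Three things are at stake. The first is missing Month 12 data that the protocol itself creates and could easily avoid. The second is an eligibility criterion that may be checked only after dosing has begun. The third is an instruction that two sites could apply differently, because the test is not named.

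**Working it through.** This is mainly a reading of text. The arithmetic in steps 5 and 6 only gives the scale.

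**1. When does the removal happen?** Consent and screening precede transplantation (Protocol 4 and Visit 1). The entry step left at Baseline is randomization, and 6.6.8 describes included patients as consented and randomized. A patient let in at Baseline and later removed is therefore removed after randomization. This holds whichever test is meant.

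**2. What happens to that patient in the analysis?** The first dose is due within 24 hours of randomization (6.6.2; Baseline Visit, item 11), so dosing will often come before the result. One dose puts the patient in the Full Analysis Set under SAP 1.2; Protocol 10.1 also asks for a valid baseline value. With no Month 12 visit, SAP 5.2 takes the last available eGFR, including an end-of-treatment visit, as the primary endpoint. Because the test must be done at once, that value could come from the first weeks after transplantation. Neither document says how these patients are to be handled.

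**3. If the test is HIV.** Section 6.4 wants every exclusion ruled out before a number is issued, whereas 7.6.4 permits entry first. HIV is in none of the serology lists: Visit 1 (HBsAg, HCV), recipient information in 7.3 (CMV, EBV, HCV, HBsAg), the laboratory list in 7.6.4 (HBsAg, HCV, CMV) and the opening of the paragraph itself (the same three).

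**4. If the tests include HCV.** The list in 6.4 cannot be chosen with HCV status unknown. Dropping HCV-positive patients would contradict the stratum, the HCV factor in the primary ANCOVA (Protocol 10.4.2, SAP 2.3.4) and the HCV evaluation in 7.5, which plans biopsies at transplantation and Month 12. SAP 5.5.1 classes anyone without a positive result as negative, so an unknown status would not show.

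**5. The plan's own sample size.** Inputs from Protocol 10.7: difference 7.0, SD 18.0, two-sided 5%, 80% power. For the two-group t-test the noncentrality is 7.0 / (18.0 × √(2/n)). At n = 105 it is 2.82 and power is 80.1%, so 105 is reproduced. Inflation: 105 / 0.8² = 164.06, rounded up to 165 per group, or 330 in all.

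**6. Scale.** The documents give neither the share u with results outstanding nor the share p of those found positive. I assume u from 1% to 10% and p from 1% to 50%. Expected removals are 330 × u × p:

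- lowest: 330 × 0.01 × 0.01 = 0.03 patients
- middle: 330 × 0.05 × 0.10 = 1.65 patients
- highest: 330 × 0.10 × 0.50 = 16.5 patients, which is 5% of 330

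If removed patients counted as lost on top of 20% drop-out, n per group is 165 × (0.80 − x), rounded down:

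| Extra loss x | n per group | Power |
|---|---|---|
| 0% | 132 | 88.3% |
| 1% | 130 | 87.8% |
| 2% | 128 | 87.3% |
| 5% | 123 | 85.9% |
| 10% | 115 | 83.6% |

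Under LOCF, dosed patients would stay in and dilute the effect instead. In the highest case, if their early values showed no treatment difference, the expected difference falls to 7.0 × 0.95 = 6.65. With 132 per group, power is then 84.9%. Both ways it stays above 80%.

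**The case against.** The strongest defence is that the rule concerns HIV alone. The HIV sentence comes directly before it, and dropping a patient for a positive result makes sense only for a virus that is excluded. HIV is the only one. On that reading there is no HCV conflict. This largely stands: HIV is the more natural reading, and the HCV conflict is only conditional. It does not remove the ambiguity, since the only tests the paragraph orders are the other three, and it does not touch the follow-up contradiction.

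A reader might infer more than the documents support:

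- **That patients will be randomized without a stratum, and that HCV-, HBsAg- or CMV-positive patients will be dropped.** This needs the less natural reading. Section 6.4 requires the stratum in order to allocate, and Visit 1 already draws HCV serology, viral load and genotype.
- **That this paragraph is the only working HIV rule.** It is not. Criterion 1 stands, and eligibility is checked at Visit 1 and again at Baseline. The missing HIV line in the schedule is supporting evidence only.
- **That the intention-to-treat analysis is broken.** Protocol 10.1 governs analysis by assigned arm. A dosed patient with a baseline value stays in the Full Analysis Set; what is lost is the Month 12 measurement.
- **That many patients are affected.** The Background's figure of at least 50% describes HCV-positive recipients in many countries. It is not a rate for these German centres, nor for patients with outstanding results.
- **That knowing the arm biases the removals.** The result is an objective laboratory finding, the rule makes no distinction by arm, and the documents show no mechanism for such bias.

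**Conclusion.** The point holds in a limited form. Removing a patient from the study after randomization contradicts Month 12 assessment of all randomized patients, whichever test is meant. For a dosed patient the consequence is an early eGFR standing in for the primary endpoint. The conflict with exclusion criterion 1 and the allocation rule holds if HIV is meant; the conflict with the HCV stratification and objectives holds only if HCV is meant.

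The size cannot be derived from the documents. The range of 0.03 to 16.5 patients rests entirely on assumed shares, and its upper end needs the HCV-type reading. If HIV is meant, the number is probably very small. No planned sample size changes. This is a matter of consistency and avoidable missing data, and it should be corrected.

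**What to change.** Amend the Viral serology paragraph of Protocol 7.6.4 and reconcile it with 5.1, 6.4, 6.6.3 and 6.6.8:

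1. Name the test or tests to which the outstanding-result rule applies.
2. State that any result bearing on eligibility or on the randomization stratum must be on file before a randomization number is issued. If HIV is such a test, show in the visit schedule where its result is obtained.
3. Replace the removal from the study with a statement that a patient found positive after randomization stays in follow-up to Month 12 and in the Full Analysis Set as randomized.
4. Reconcile separately what happens to study drug and care in such a patient. The current text refers to the center's standard care, and that clinical decision is for the sponsor to state.

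The cost is amendment wording and one filed result per patient before randomization. Delay should be slight: tests up to 6 months old are already accepted, and randomization is at least 7 days after transplantation. SAP 2.2.1 already tabulates reasons for discontinuation, so counting any removals under this rule by arm would supply the figure the documents lack.

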### **New onset diabetes mellitus (NODM)**

The incidence of NODM will be assessed from Day 30 post-transplantation. NODM post-transplantation, in patients without diabetic history, is defined by any of the following:

- Two consecutive fasting plasma glucose levels  $\geq 126$  mg/dL (7.0 mmol/L) post-transplantation ( $> 30$  days).
- HbA1c  $\geq 6.5$  % from Day 75 onward.
- Diabetes mellitus (DM) reported as an adverse event that is prevalent after Day 30.
- Any concomitant medication with ATC level 2 code “A10” drugs used in diabetes, if prevalent after Day 30 and used for more than 30 days.

Non-diabetic patients, identified at the time of transplantation by all the following:

- DM or diabetic related terms were not included in medical history.
- Glucose (random)  $< 11$  mmol/L at the time of transplantation.
- HbA1c  $< 6.5$  % at the time of transplantation.

In addition, incidence of patients that are pre-diabetic will be assessed using an HbA1c range of 5.7 to 6.4%.

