### **Baseline Visit - Visit 2 (day 1)**

The Baseline assessment has to be performed prior to randomization.

1. Patient's eligibility for the study according to in- and exclusion criteria will be checked.
2. A complete physical examination will be performed.
3. Vital signs will be measured.
4. Urinalysis will be performed.
5. Venous blood will be drawn for measurement of hematology and biochemistry.
6. Glomerular Filtration Rate (GFR) will be calculated.
7. Venous blood will be drawn for HCV monitoring: Viral load (RNA level), in HCV positive patients only.
8. Venous blood will be drawn for measurement of the tacrolimus C0-h blood levels.
9. Prior/Concomitant medications / significant non-drug therapies will be recorded.
10. Patients eligible for the study will be randomized to one of the two treatment groups.
11. Study drug intake will be performed within 24h.
12. Information on rejection episodes biopsies, hospitalization, infections, and other (S)AEs that occurred since the last visit will be recorded.

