### **2.6.1 Adverse events (AEs)**

Treatment emergent events are defined as all adverse events started at baseline or later.

Treatment emergent adverse events were summarized by presenting, for each treatment group, the number and percentage of patients having any adverse event, having an adverse event in

each body system and having each individual adverse event. Any other information collected (e.g. severity or relatedness to study medication) were listed as appropriate.

Data collected by AE CRFs and by Infection CRFs were coded using MedDRA. The number of AE/patients with AE was summarized by MedDRA system organ class and preferred term. Additionally, AE will be summarized

- by maximum severity,
- for AE with suspected drug relation,
- for serious AE (SAE), and
- for AE leading to permanent discontinuation of study drug.

In addition to being analyzed together with AE data, the incidence of bacterial, viral and fungal infections will be tabulated separately for all infections

- by maximum severity,
- for infections with suspected drug relation,
- for serious infections and
- for infections leading to premature discontinuation of study drug.

Infections were defined as adverse events as adverse events in primary system organ class “Infections and infestations”.

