## 4 Change to protocol specified analyses

The study protocol was amended 5 times, the original protocol and all amendments are provided in [Appendix 16.1.1](#). Previous sections of this report describe the study conduct as amended. The key features of each amendment are given below:

**Amendment 1** (20-Jan2012), before generation of CRF and inclusion of first, introduced the following changes:

- Assessment schedule: Laboratory and GFR were shifted from Screening visit to baseline visit
- Additional assessment in Screening visit: Menopausal status and in all women of childbearing potential a pregnancy test

**Amendment 2** (26-Sep-2012), 15 patient had been randomized to the study. The major changes that were made to the protocol were as follows:

- Measurement of the Tacrolimus C-0h levels can now be performed as per local practice.
- Inclusion criteria – randomization 2 was rephrased for a clearer understanding.

- Inclusion criteria – randomization 3: AST and ALT levels were raised to  $\leq 5$  times ULN, evaluation of gamma GT was deleted due to the fact that it does not reflect a prognostically important mark.
- For a better understanding, exclusion criteria – randomization 2 was separated in 4 independent criteria. Platelet, neutrophil and white blood cell count was reduced to 50,000/mm^3, 1,000/mm^3 and 2,000/mm^3 respectively
- Former inclusion criteria – randomization 2 (now 6): Calculation mistake of concentration of hypertriglyceridemia was corrected.
- Graft loss was added as reason for premature patient withdrawal.
- Dispensing of study drug and instruction for use of study drug are described in more detail to avoid misuse.
- According to the adaptation of in- and exclusion criteria, the permission of study drug adjustment and interruption in case of inability of tolerance of the protocol-specific dosing scheme is described in more detail.
- PCP prophylaxis and treatment of oral candida will be performed according to local practice.
- It was added, that pregnancy outcomes must be collected for the female partners of any males who took study drug in this study

These amendments were not considered to have affected the interpretation of study results as they were minor.

**Amendment 3** (14-JUN2013): 57 patients had been randomized to the study:

Five sub-studies which will be conducted in selected centers were added to the protocol. In addition some editorial changes were performed.

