New onset diabetes mellitus	PT contains “Diabetes Mellitus” as Adverse event, but no PT containing “Diabetes Mellitus” as medical history
Hepatocellular Carcinoma (HCC)	HLT “HEPATIC NEOPLASMS MALIGNANT” OR “HEPATOBILIARY NEOPLASMS MALIGNANT UNSPECIFIED”
De novo HCC malignancies	HLT “HEPATIC NEOPLASMS MALIGNANT” OR “HEPATOBILIARY NEOPLASMS MALIGNANT UNSPECIFIED” as adverse event, but no HLT “HEPATIC NEOPLASMS MALIGNANT” OR “HEPATOBILIARY NEOPLASMS MALIGNANT UNSPECIFIED” as medical history

**Concomitant therapy of special interest** were defined as followed.

Concomitant therapy of special interest	Identification
Renal replacement therapy	PT „NON-DRUG THERPY: DIALYSIS“ or ATC CODE “B05Z (HEMODIALYTICS AND HEMOFILTRATES”

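### New onset diabetes: the protocol's non-diabetic rule needs laboratory values that no visit schedules, and separately the SAP names no at-risk denominator for the percentage

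*Protocol*

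**What the plan says.** **Protocol, at-risk rule.** Section 7.6.4 (New onset diabetes mellitus) applies the NODM definition to patients without diabetic history. It then sets out "Non-diabetic patients, identified at the time of transplantation by all the following". There are three conditions and all must hold:

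- "DM or diabetic related terms were not included in medical history";
- random glucose below 11 "mmol/L at the time of transplantation";
- HbA1c below 6.5%, also at transplantation.

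**Protocol, schedule.** The Visit 1 list orders blood for viral serology, CMV and HCV monitoring and a pregnancy test, but no biochemistry. Table 2 has no mark for hematology/biochemistry at Screening. The first such item is at Visit 2: "Venous blood will be drawn for measurement of hematology and biochemistry". Visit 2 falls 7-21 days after transplantation. SAP section 4 gives the reason, in its account of Amendment 1: "Laboratory and GFR were shifted from Screening visit to baseline visit". The panel in protocol 7.6.4 contains HbA1c (printed Hb1c) and fasting glucose; random glucose is not in it.

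**SAP, numerator.** The table of adverse events of special interest in 5.5.2 identifies NODM by a preferred term containing diabetes mellitus "as Adverse event, but no PT containing" that term in the medical history.

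**SAP, measure.** Section 2.6.1 summarises treatment-emergent events, for each treatment group, as "the number and percentage of patients having any adverse event", and likewise by body system and by individual event. Section 2.6.1.1 lists NODM among the events of special interest without a denominator. The one NODM subset it defines is patients with baseline HbA1c of 5.7 to 6.4%.

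**The concern.** There are two separate problems.

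First, the protocol's rule for who is at risk depends on two measurements at a time when no visit collects them. Visit 2 values are not a ready substitute. They are taken at least a week after transplantation, with corticosteroids already started under protocol section 4, and the glucose is fasting rather than random. No text says that they may stand in.

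Second, an incidence proportion needs a denominator of patients who could have the event. The SAP takes patients with a diabetes history out of the numerator and says nothing about taking them out of the denominator. Diabetes is not an exclusion criterion at enrollment or at randomization, so such patients can be in the trial.

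NODM incidence is a named safety objective in both documents. If the text is followed literally, the reported incidence and the absolute difference between arms are both too small, which for a safety outcome is not the cautious direction.

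**Working it through.** **Part 1: can the at-risk rule be applied from scheduled data?**

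| Condition (all required) | Scheduled source |
|---|---|
| No diabetes in medical history | Yes: history is recorded from Visit 1 up to randomization |
| Random glucose below 11 mmol/L at transplantation | None: first biochemistry at Visit 2, fasting glucose only |
| HbA1c below 6.5% at transplantation | None: first HbA1c at Visit 2 |

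Two of the three conditions have no scheduled source, so no patient can be shown from scheduled data to meet the rule. The history condition can be applied to everyone.

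**Part 2: size of the dilution**

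Inputs:

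- Patients per arm: 165 (protocol 10.7, SAP section 3). This reproduces: 105/(1 - 0.20)² = 164.06, rounded up to 165. It serves here only as the all-patients denominator; the safety set may be smaller.
- Share of an arm with known diabetes, q: not in the documents. Assumed 10% to 40%.
- True incidence among patients at risk, p: not in the documents. Illustrated with 25% and 15%.

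Patients with known diabetes cannot be cases, so events = p × (1 - q) × 165. Dividing by 165:

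reported percentage = p × (1 - q).

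| q (assumed) | At risk, of 165 | True 25% reported as | True 15% reported as | True 10-point difference reported as | Risk ratio (15% v 25%) |
|---|---|---|---|---|---|
| 10% | 148.5 | 22.5% | 13.5% | 9 points | 0.60 |
| 20% | 132 | 20.0% | 12.0% | 8 points | 0.60 |
| 30% | 115.5 | 17.5% | 10.5% | 7 points | 0.60 |
| 40% | 99 | 15.0% | 9.0% | 6 points | 0.60 |

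With the same q in both arms, (1 - q) cancels from the ratio but not from the incidence or the difference.

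**Part 3: unequal q by chance**

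Randomization is stratified by HCV status and lab MELD, not by diabetes, so q can differ between arms by chance. At q = 25% and 165 per arm, one standard deviation of the prevalence difference is √(2 × 0.25 × 0.75/165) = 0.048, or 4.8 points. With a true incidence of 25% in both arms this moves the reported difference by 0.25 × 4.8 = 1.2 points.

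A larger case is 20% v 30%. The reported rates are 0.25 × 0.80 = 20.0% and 0.25 × 0.70 = 17.5%, a ratio of 0.875.

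- The prevalence gap of 10 points has a standard error of √((0.20 × 0.80 + 0.30 × 0.70)/165) = 4.7 points, so it is about 2.1 standard errors and an unusual draw.
- The resulting 2.5-point difference in NODM compares with a standard error of √((0.20 × 0.80 + 0.175 × 0.825)/165) = 4.3 points, so it is about 0.6 of one standard error.

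**The case against.** **The denominator is inferred.** No sentence in the SAP gives the NODM denominator. The 2.6.1 wording is the general AE rule, and the 5.5.2 table only identifies cases. The SAP says that it implements the protocol's planned analysis, the protocol confines NODM to patients without diabetic history, and the mock tables, which are not among these documents, may apply that restriction. This stands as a limit: the SAP is silent and does not positively choose an all-patients denominator. It does not remove the point, because the only stated measure is per treatment group and a denominator belongs in the SAP.

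**The two problems are not cause and effect.** A reader might infer that the missing glucose and HbA1c values produce the dilution. They do not. The SAP's case rule uses history alone, and the dilution would arise even if both values had been collected.

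**Unscheduled is not the same as absent.** Lab MELD is described as measured at screening although Table 2 has no row for it, so some pre-transplant laboratory information reached the study outside the schedule. This shows that local values may exist for some patients. It supplies neither glucose nor HbA1c, and the finding is limited to scheduled data.

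**Chance imbalance is not bias.** A reader might infer that unequal prior diabetes would create a false treatment effect. Diabetes at transplantation precedes randomization, so imbalance is ordinary sampling error, and Part 3 shows that it is small. No between-arm test of NODM is specified. This objection stands in full; the harm is the understated incidence and absolute difference.

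**Conclusion.** Both points hold, as separate points.

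1. The protocol's non-diabetic rule cannot be applied from scheduled data, because random glucose and HbA1c at transplantation are not collected at any visit.
2. Read as written, the SAP understates NODM incidence by the factor (1 - q). At equal prevalence it understates the risk difference by the same factor and leaves the risk ratio unchanged. For an assumed q of 10-40% this is a relative understatement of 10-40%: a true 25% appears as 22.5% down to 15%.

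The size rests on assumed prevalence and incidence, and on reading the SAP's silence literally. The documents do not support the stronger reading that the plan biases the comparison between arms.

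The matter is minor. NODM is a descriptive secondary safety outcome, and the primary analysis and sample size are unaffected.

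**What to change.** In the SAP:

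- State that every NODM percentage uses, by arm, safety-set patients with no diabetes term in medical history. Apply one list of history terms to both numerator and denominator; the protocol's wording (diabetes or diabetes-related terms) is wider than the SAP's.
- Exclude in addition patients with pre-transplant use of an ATC A10 drug where it is recorded. This can only supplement history: protocol 6.6.5 requires listing of medication given after the screening visit, so earlier use may be incomplete.
- State that the two laboratory conditions at transplantation cannot be applied from scheduled data. Use local pre-transplant glucose or HbA1c, where available, only in a sensitivity analysis.
- List the change in section 4, whose list of changes in statistical methods does not mention NODM.

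The cost is SAP wording and a changed denominator in the NODM tables, with no new data. The downside is that, without the laboratory conditions, some undiagnosed pre-existing diabetes may count as new onset; the SAP should say so.
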